10.5.3 Trial Procedures

10.5.3.1 Safety Assessments

10.5.3.1.1 Vital Signs

Blood pressure, heart rate, and weight will all be measured as described in the protocol at the time points defined in this Schedule of Assessments - Trial Continuity (Table 10.5.1.2-1) with the following changes, if remote visits are necessary:

• Subjects will be asked to use their own collection device, if available, until devices can be provided to subjects;

- Site staff will remotely supervise the collection of measurements via video or guide by telephone, if video is not possible.
- All remote measurements should be performed at a consistent time of day.
- Site staff will be instructed to record the measurement in the source system, and if
 there are believed to be any errors, inconsistencies, or safety concerns with the
 home measurement, the medical monitor should be notified.
- Site staff will instruct the subjects to follow the procedures in the protocol for blood pressure and heart rate collection.

10.5.3.1.2 **Pregnancy**

Pregnancy tests will be performed as described in the protocol at the time points defined in this Schedule of Assessments - Trial Continuity (Table 10.5.1.2-1) with the following changes:

- For the baseline visit that requires a pregnancy test for FOCBP, the site will provide the necessary tests and instructions so the test may be performed at home;
- Applicable subjects will perform a pregnancy test prior to dosing with IMP, ensuring
 a date and time-stamped picture or video of the result is taken, followed by
 notification to the site staff of the results via telephone, or other means, on the
 appropriate visits. Subjects will also provide the site staff with the date- and time
 stamped picture/video.
 - If negative, site to inform subject to proceed with dosing.
 - If positive, the site must instruct the subject to immediately stop taking IMP, and the site will refer to the Pregnancy section of the protocol for appropriate IRE reporting.
 - Further instruction must be agreed upon in consultation with the sponsor.

11 References

- ² Saltiel P, Silvershein D. Major depressive disorder: mechanism-based prescribing for personalized medicine. Neuropsychiatr Dis Treat. 2015;11:875-888.

#### 1 Introduction

This statistical analysis plan (SAP) documents the statistical methodology and data analysis algorithms and conventions to be applied for statistical analysis and reporting of efficacy and safety data of study 331-201-00289. All amendments to the protocol are taken into consideration in developing this SAP.

## 2 Trial Objectives

The primary objective of the trial is:

 To prospectively characterize the effect of brexpiprazole on the concept of engagement, by evaluating Inventory of Depressive Symptomatology Self-Report (IDS-SR)-10-engagement, and the IDS-SR Total score, in patients with MDD with a current depressive episode.

The secondary objectives of the trial are:

- To evaluate patients' impression of improvement of their depression symptoms over time.
- To explore the relationship between engagement and other clinical effects of brexpiprazole, such as improvement in depressive symptoms and functioning.
- To evaluate the safety and tolerability of brexpiprazole (flexible dose; 0.5 to 2 mg once daily [QD]) as adjunctive therapy to antidepressant therapy (ADT) in the proposed patient population with MDD.

## 3 Trial Design

### 3.1 Type/Design of Trial

This is a phase 4, multicenter, open-label, flexible dose trial designed to assess the effects of brexpiprazole (flexible dose; 0.5 to 2 mg QD) as adjunctive therapy to ADT in patients with MDD. This trial is being conducted in line with the Canadian Product Monograph.

The trial will be organized as follows:

Screening Phase: The screening period of up to 14 days (Days -14 to -1) will begin when the informed consent form (ICF) is signed. The purpose of the screening period is to assess eligibility criteria at 1 or more visits (as necessary to complete screening assessments) and to washout prohibited concomitant pharmacotherapy, if applicable.

Open-Label Treatment Phase: Patients meeting all of the inclusion and none of the exclusion criteria will be enrolled at the baseline visit into an 8-week open-label treatment phase. The

5

[figure not shown]
Confidential - Proprietary Information

SAP 331-201-00289

screening and baseline visits can occur on the same day if the patient meets all required enrollment criteria. During the open-label treatment phase, all patients will receive brexpiprazole (that is, adjunctive brexpiprazole as a flexible dose; 0.5 to 2 mg/day) and will continue on the stable dose of ADT that they were taking at screening. Patients will attend visits at Weeks 2, 4, and 8 during the open-label treatment phase. If any patient discontinues the trial early, every effort should be made to complete the Week 8/early termination (ET) evaluations.

A schematic of the trial design is presented in Figure 3.1-1.

Version Date: 29 Jun 2022

N = number of patients.

Figure 3.1-1 Trial Design Schematic

<sup>aThe screening visit can comprise 1 or more visits as needed. The screening and baseline visits can occur the same day if the patient meets all required enrollment criteria.

<sup>bPatient diary entries will be reduced in frequency from daily to twice weekly from the day after the Week 4 visit to Week 8 (word of the day and PGI-S).

SAP 331-201-00289

#### 3.2 **Trial Treatments**

Treatment will consist of open-label brexpiprazole plus an ADT. The investigator must be able and willing to prescribe brexpiprazole to the patient per the approved Canadian Product Monograph. Brexpiprazole should be taken at approximately the same time each day and can be taken at the same time as the ADT. Antidepressant therapy is not considered trial drug in this trial. The dosing schedule for brexpiprazole is presented in Table 3.2-1.

Table 3.2-1 Brexpiprazole Dosing Schedule			
Trial Days	Week	Brexpiprazole Adjunctive Therapy a	
1-7	1	Starting dose: Single oral 0.5 or 1 mg tablet QD.	
8-14	2	Up-titration at weekly intervals QD achieved by/at Week 2.	
15-21	3		
22-28	4	g: 1 1 () OD	
29-35	5	Single oral (s) QD.	
36-42	6	(Dose increases must occur at weekly intervals. The	
43-49	7	maximum recommended target dose is 2 mg QD).	
50-56	8		

<sup>aBrexpiprazole tablet strengths are 0.25, 0.5, 1, and 2 mg per the Canadian Product Monograph.

Patients will take the first dose of brexpiprazole with or without food on the day after they are enrolled in the trial (Day 1). In accordance with the Canadian Product Monograph, the starting dose will be 0.5 mg or 1 mg QD. Up-titration will occur at weekly intervals to reach a dose of at least 1 mg QD by the Week 2 visit. After the Week 2 visit, the dose may be decreased to a minimum of 0.5 mg QD or increased to a maximum of 2 mg QD based on the investigator's clinical judgment. Dose increases may occur at weekly intervals based on the patient's clinical response and tolerability. Dose decreases can occur at unscheduled trial visits. This dosing regimen is consistent with the Canadian Product Monograph and with clinical practice in Canada.

Allowable brexpiprazole doses that may be given starting the day after the Week 2 visit will be QD. The dose of 2 mg QD is the recommended target dose and is also the maximum recommended dose.

#### 3.3 **Trial Population**

The trial population will include male and female outpatients between the regional age of majority (18 or 19 years of age) and 65 years of age, inclusive, with a Diagnostic and

Statistical Manual of Mental Disorders, 5th Edition (DSM-5) diagnosis of a single or recurrent, non-psychotic episode of MDD with or without symptoms of anxiety. Additionally, patients must have a treatment history for the current major depressive episode (MDE) of an inadequate response (assessment of inadequate response is per investigator judgment) to at least 1 and no more than 2 adequate antidepressant treatments (including the antidepressant that the patient is taking at screening).

Patients with a historical diagnosis of any concurrent condition that is exclusionary may be permitted if the investigator determines and documents this prior diagnosis was not appropriate based on current and historical presentation.

Patients with ADHD, obsessive compulsive disorder (OCD), panic disorders, or generalized anxiety disorder can be included under the following conditions:

- These disorders are not the primary focus of treatment at the screening visit
- Changes in any treatment for these disorders (permitted medication and/or psychotherapy) would not likely be required for the duration of the trial
- All other concurrent psychiatric or neurological diagnoses must be discussed with the medical monitor.

#### 4 Sample Size

This is a single-arm trial to assess the effect of brexpiprazole on patient engagement in MDD patients through the following co-primary endpoints: 1) change from baseline to Week 8 in IDS-SR-10-engagement; 2) change from baseline to Week 8 in IDS-SR Total score.

Based on the results of the appropriate brexpiprazole-plus-ADT arms from four previous Phase 2/3 brexpiprazole MDD trials, it is reasonable to expect a mean change of -2.5 (standard deviation = 6.5) in IDS-SR-10-engagement and a mean change of -5 (standard deviation = 13.5) in IDS-SR Total score from baseline to Week 8. A sample size of 100 completers (ie, patients who have an evaluation on IDS-SR Total score and IDS-SR-10-engagement at Week 8) will yield 95% power to show a difference from baseline in IDS-SR Total score and at least 95% power to show a difference from baseline in IDS-SR-10-engagement at a two-sided significance level of 0.05, respectively. It will ensure the overall power is at least 90%. After considering an ET rate of 25%, a total of 134 patients needs to be enrolled in this trial.

It is anticipated that approximately 210 patients will be screened in order to enroll 134 subjects from approximately 15 sites (to complete 100 patients).

## 5 Statistical Analysis Datasets

### 5.1 Datasets for Analysis

The following analysis samples are defined for this trial:

Enrolled Sample: comprises all patients who signed an ICF for the trial and enrolled into the open-label treatment phase.

Safety Sample: comprises all enrolled patients who received at least one dose of open-label brexpiprazole.

Efficacy Sample: the Full Analysis Set comprises all patients in the Safety Sample who have a baseline value and at least one post-baseline efficacy evaluation for IDS-SR Total score and IDS-SR-10-engagement during the open-label treatment phase.

Per-Protocol Sample: Comprises all patients in the Efficacy Sample which excludes major protocol deviation subjects.

### 5.2 Handling of Missing Data

IDS-SR is utilized as the primary efficacy measurement to assess core diagnostic depressive symptoms as well as the atypical and melancholic symptom features of MDD. The IDS-SR consists of 30 items, all rated on a 0 to 3 scale with 0 being the "best" rating and 3 being the "worse" rating. Besides item 9, two sub-items 9A and 9B exist, with possible scores of 1, 2 or 3 for item 9A, and 0 or 1 for item 9B. The scores for these two sub-items are not included in the calculation of the total score. Item 11 or item 12 should be completed but not both, and similarly, item 13 or item 14 should be completed but not both. Should items 11 and 12 be rated both, then the maximum of the two scores will be used. The same approach will be used for handling items 13 and 14.

The IDS-SR Total Score is the sum of ratings of 28 item scores. The possible IDS-SR Total Score ranges from 0 to 84. The IDS-SR Total Score will be un-evaluable if less than 23 of the 28 items are recorded. If the number of items recorded is at least 23 and at most 27, the IDS-SR Total Score will be the mean of the recorded items multiplied by 28 and then rounded to the first decimal place.

The IDS-SR-10-engagement is the sum of ratings of the selected 10 item scores, including item 8 - Response of your mood to good or desired events, item 15 - Concentration/decision making, item 16 - View of myself, item 17 - View of my future, item 19 - General interest, item 20 - Energy level, item 21 - Capacity for pleasure or enjoyment (excluding sex), item 22 - Interest in sex (please rate interest, not activity),

item 23 - Feeling slowed down, and item 29 - Interpersonal sensitivity. The possible IDS-SR-10-engagement ranges from 0 to 30. The IDS-SR engagement score will be unevaluable if less than 8 of the 10 items are recorded. If 8 or 9 of the 10 items are recorded, the IDS-SR engagement score will be the mean of the recorded items multiplied by 10 and then rounded to the first decimal place.

The observed-cases (OC) data set will consist of actual observations recorded at each scheduled visit during the open-label treatment phase, and no missing data will be imputed. MMRM analysis will be performed on the OC dataset.

The last observation carried forward (LOCF) approach will also be used to impute missing data for continuous and categorical efficacy endpoints. The LOCF data set will include data recorded at a scheduled visit during the open-label treatment phase or, if no observation is recorded at that visit, data carried forward from the previous scheduled visit at the open-label treatment phase. Baseline data will not be carried forward to impute missing values for the LOCF data set.

#### 5.3 Definition of Baseline and Last Visit

Baseline is defined as the last available measurement prior to the first dose of open-label brexpiprazole, while last visit is defined as the last available measurement upon completion or early termination of the open-label treatment phase.

#### 6 Outcome Variables

### 6.1 Efficacy Variables

The efficacy of open-label brexpiprazole is assessed by IDS-SR, Patient Health Questionnaire 9-item (PHQ-9), Generalized Anxiety Disorder 7-item scale (GAD-7), World Health Organization Disability Assessment Schedule (WHODAS) 2.0 short form questionnaire, Sheehan Disability Scale (SDS), Clinical Global Impression - Severity (CGI-S), Clinical Global Impression - Improvement (CGI-I), Patient Global Impression - Severity (PGI-S), Patient Global Impression - Improvement (PGI-I) scales, and 'Word of the Day'.

### 6.2 Safety Variables

The safety of the open-label brexpiprazole is assessed based on reported adverse events (AEs), vital signs, body weight, BMI, and physical examination,

## 7 Disposition and Demographic Analysis

### 7.1 Subject Disposition

Subject disposition, subject completion rate and reasons for discontinuation will be summarized for the Enrolled Sample.

### 7.2 Demographic and Baseline Characteristics

Baseline demographic characteristics, including age, race, ethnicity, gender, weight, height, and BMI for the Enrolled Sample, will be summarized. Summary statistics will consist of mean, median, minimum, maximum, and standard deviation for continuous variables and tabulations of frequency distributions for categorical variables.

Baseline disease characteristics will also be summarized for the Enrolled Sample by summary statistics. They include IDS-SR related assessments, PHQ-9 total score, GAD-7 total score, WHODAS 2.0 short form score, SDS score, CGI-S score, PGI-S score. and 'Word of the Day'.

### 7.3 Medical and Psychiatric History

A summary of medical and psychiatric history will be presented for the Enrolled Sample. Listings of medical and psychiatric history will also be provided.

#### 7.4 Treatment Compliance

Based on the Study Medication Log of the CRF, compliance in taking study medication is calculated by the dividing total dose taken by the total dose prescribed for subjects during the open-label treatment period. A listing of treatment compliance by subject will be provided on the Safety Sample.

#### 7.5 Concomitant Medications

Number and proportion of subjects taking concomitant medications prior to, during, and post the open-label treatment period will be tabulated by drug classification using the World Health Organization (WHO) drug dictionary on the Safety Sample. In addition, listings of concomitant mediations will be provided.

#### 7.6 Protocol Deviations

Protocol deviation data will be summarized by type of deviations and center. In addition, listing will be provided describing the deviations by subject.

## 8 Efficacy Analysis

All efficacy analyses pertaining to open-label treatment period will performed on the Efficacy Sample. Statistical comparisons are based on 2-sided, 0.05 significance levels.

### 8.1 Primary Efficacy Endpoint

The co-primary efficacy endpoints are as follows:

- 1) Change from baseline to Week 8 in IDS-SR-10-engagement
- 2) Change from baseline to Week 8 in IDS-SR Total score

### 8.1.1 Technical Computation Details for Primary Efficacy Analysis

The primary hypothesis is that the mean changes from baseline to Week 8 in both coprimary endpoints will differ from 0, separately. Each of the endpoints will be tested by fitting a MMRM analysis with an unstructured variance covariance structure at a two-sided significance level of 0.05 on OC dataset on Efficacy Sample. The model will include fixed effect terms for visit, baseline value, an interaction term of baseline value by visit, and trial center. The trial will be claimed positive if both p-values are less than 0.05. Therefore, the overall type I error is controlled at 0.05 level.

In case there is a convergence problem with MMRM model with the unstructured variance covariance matrix, the following structures other than unstructured will be used in order of 1) heterogeneous Toeplitz, 2) heterogeneous autoregressive of order 1, and 3) heterogeneous compound symmetry and the first (co)variance structure converging to the

best fit will be used as the primary analysis. If a structured covariance has to be used, the "sandwich" estimator of the standard error of the fixed effects parameters will be used in order to deal with possible model misspecification of the covariance matrix.

The SAS code for the PROC MIXED procedure to carry out the above MMRM analysis with an unstructured variance covariance structure is illustrated as follows:

where baseline is the last IDS-SR assessment total score at baseline.

[figure not shown]
#### 8.2 Other Efficacy Endpoint Analysis

The other efficacy endpoints are as follows. All of them will be evaluated at a nominal 0.05 level (2-sided) without adjusting for multiplicity on Efficacy Sample:

[figure not shown]
- 1) Change from baseline to Weeks 2 and 4 in IDS-SR-10-engagement
- 2) Change from baseline to Weeks 2 and 4 in IDS-SR Total score
- 3) Change from baseline to Weeks 2, 4, and 8 in IDS-SR patient-selected engagement items
- 4) Change from baseline to Weeks 2, 4, and 8 in IDS-SR engagement items selected by both clinicians and patients.
- 5) Change from baseline to Weeks 2, 4, and 8 in CGI-S score
- 6) CGI-I score at Weeks 2, 4, and 8
- 7) Change from baseline to Weeks 4 and 8 in SDS Mean score and SDS individual item scores
- 8) Change from baseline to Weeks 4 and 8 in WHODAS 2.0 short form score.
- 9) Change from baseline to Weeks 2, 4, and 8 in PHQ-9 score
- 10) Change from baseline to Weeks 2, 4, and 8 in GAD-7 score
- 11) PGI-I score at each timepoint (ie, being measured weekly at home)

- 12) PGI-I response rate at each timepoint (ie, being measured weekly at home), where response is defined as a PGI-I score of 1 or 2 (very much improved or much improved)
- 13) Time to first PGI-S response, where response is defined as a reduction of 2 points in PGI-S score from baseline.

Endpoint (1) - (5), (7) - (10) will be analyzed by fitting the same MMRM model described in the primary analysis on OC dataset. Endpoints (6) and (11) will be analyzed using one-sample t-test on LOCF dataset, with the null hypothesis of no change in each of the endpoints. The point estimate with 95% CI will be provided for endpoint (12) using normal approximation on LOCF dataset. Endpoint (13) will be evaluated by time-to-event analysis with Kaplan-Meier curve on OC dataset. The time origin for measuring this event time is the date of the first dose of open-label brexpiprazole. The event date will be the date when a reduction of 2 points in PGI-S score from baseline is achieved.

Version Date: 29 Jun 2022

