The observed cases (OC) data set will consist of actual observations recorded at each scheduled visit during the open-label treatment phase, and no missing data will be imputed. MMRM and sensitivity analyses based on MNAR will be performed on the OC dataset. The last observation carried forward (LOCF) approach will also be used to impute missing data for continuous and categorical efficacy endpoints. The LOCF data set will include data recorded at a scheduled visit during the open-label treatment phase or, if no observation is recorded at that visit, data carried forward from the previous scheduled visit at the open-label treatment phase. Baseline data will not be carried forward to impute missing values for the LOCF data set.

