9.4.1.3 Other Efficacy Endpoint Analysis

The other efficacy endpoints are as follows. All of them will be evaluated at a nominal 0.05 level (2-sided) without adjusting for multiplicity on Efficacy Sample:

- 1) Change from baseline to Weeks 2 and 4 in IDS-SR-10-engagement.
- 2) Change from baseline to Weeks 2 and 4 in IDS-SR Total score.
- 3) Change from baseline to Weeks 2, 4, and 8 in IDS-SR patient-selected engagement items.
- 4) Change from baseline to Weeks 2, 4, and 8 in IDS-SR engagement items selected by both clinicians and patients.
- 5) Change from baseline to Weeks 2, 4, and 8 in CGI-S score.
- 6) CGI-I score at Weeks 2, 4, and 8.
- 7) Change from baseline to Weeks 4 and 8 in SDS Mean score and SDS individual item scores.
- 8) Change from baseline to Weeks 4 and 8 in WHODAS 2.0 short form score.
- 9) Change from baseline to Weeks 2, 4, and 8 in PHQ-9 score.
- 10) Change from baseline to Weeks 2, 4, and 8 in GAD-7 score.
- 11) Change from baseline to each timepoint (ie, being measured weekly at home) in depression as measured by PGI-I score.

- 12) PGI-I response rate at each timepoint (ie, being measured weekly at home), where response is defined as a PGI-I score of 1 or 2 (very much improved or much improved).
- 13) Time to first PGI-S response, where response is defined as a reduction of 2 points in PGI-S score from baseline.

Endpoint (1) - (5), (7) - (11) will be analyzed by fitting the same MMRM model described in the primary analysis on OC dataset. Endpoint (6) will be analyzed using one-sample t-test on LOCF dataset. Endpoint (12) will be evaluated using descriptive statistics on LOCF dataset. Endpoint (13) will be evaluated by time-to-event analysis with Kaplan-Meier curve on OC dataset.

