#### Patient Global Impression - Improvement (PGI-I) 11.2.12

The Patient Global Impression – Improvement (PGI-I) scale is a 7-point single-item self report scale depicting a patient's rating of overall improvement in their condition since starting trial medication. Patients answer the following question: "Since starting trial medication, how much have your symptoms of Major Depressive Disorder changed?" Scores range from 1 "very much improved" to 7 "very much worse." The PGI-I will be administered weekly throughout the trial.

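### SAP 8.2 moves weekly PGI-I from the protocol's observed-case MMRM to a t-test on LOCF data, and SAP Section 10 does not record the change

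*SAP*

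**What the plan says.** Protocol 9.4.1.3 defines endpoint 11 as "Change from baseline to each timepoint (ie, being measured weekly at home) in depression as measured by PGI-I score" and assigns the method as follows: "Endpoint (1) - (5), (7) - (11) will be analyzed by fitting the same MMRM model described in the primary analysis", on the observed-case (OC) dataset. It gives the one-sample t-test on LOCF data to endpoint 6 (CGI-I) alone, and LOCF descriptive statistics to endpoint 12 (PGI-I response rate).

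SAP 8.2 renames endpoint 11 as the PGI-I score at each timepoint, ends the MMRM group at endpoint 10, and states: "Endpoints (6) and (11) will be analyzed using one-sample t-test on LOCF dataset", with a null hypothesis of no change. SAP Section 10, the heading for changes in the planned analyses, reports none. SAP 8.4 adds a sensitivity analysis for the primary endpoint only, so the text supplied contains no observed-case companion for PGI-I.

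On LOCF in general, Protocol 9.3 says: "The last observation carried forward (LOCF) approach will also be used to impute missing data for continuous and categorical efficacy endpoints".

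**The concern.** The endpoint's definition, model and missing-data method all differ between the two documents, and the section meant to say so is empty. A reader of the SAP would take the LOCF t-test to be the protocol's plan.

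PGI-I is the scale closest in wording to the first secondary objective, patients' "impression of improvement of their depression symptoms over time". The weekly curve is therefore the result of interest, and LOCF acts directly on it: each early leaver's last rating is held fixed for all remaining weeks. If ratings are still changing when patients leave, the late means shift and the time course is usually flattened.

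A smaller gap is that the SAP tests no change without giving the PGI-I value this corresponds to. It labels only scores 1 and 7 for PGI-I, whereas for CGI-I it labels 4 as no change.

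**Working it through.** **Side by side**

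| | Protocol 9.4.1.3 | SAP 8.2 |
|---|---|---|
| Endpoint 11 | Change from baseline in PGI-I | PGI-I score |
| Method | MMRM | One-sample t-test |
| Dataset | OC | LOCF |

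**What the missing baseline justifies.** The PGI-I question is "Since starting trial medication, how much have your symptoms of Major Depressive Disorder changed", so no pre-dose rating exists. For the primary model, "The model will include fixed effect terms for visit, baseline value, an interaction term of baseline value by visit, and trial center". The two baseline terms cannot be fitted to PGI-I. Visit and center can, on observed cases. Removing the baseline terms and rewording the endpoint follow from the scale; changing the missing-data method does not.

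**The plan's own figures.** Neither document gives a PGI-I mean, SD or trajectory. The dropout figure reproduces: 100 completers/(1 - 0.25) = 133.3, rounded up to 134.

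**Illustration (assumed).** Mean PGI-I is 4 at Week 0 and falls by 0.15 a week to 2.80 at Week 8. 25% leave, with last ratings spread evenly over Weeks 1 to 7 and unrelated to the rating.

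- Mean last rating of leavers: (3.85 + 3.70 + 3.55 + 3.40 + 3.25 + 3.10 + 2.95)/7 = 3.40.
- LOCF Week 8: 0.75 x 2.80 + 0.25 x 3.40 = 2.95. Loss: (2.95 - 2.80)/1.20 = 12.5%.
- LOCF Week 4: 3.40 + (0.25/7) x (0.45 + 0.30 + 0.15) = 3.43, against 3.40.
- LOCF Week 6: 3.10 + (0.25/7) x (0.75 + 0.60 + 0.45 + 0.30 + 0.15) = 3.18, against 3.10.

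The error grows with time.

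**Range at Week 8, dropout unrelated to rating**

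- Linear path, all leavers' last ratings in Weeks 1-3: 0.75 x 2.80 + 0.25 x 3.70 = 3.025; 18.75% lost.
- Improvement complete by Week 4, last ratings over Weeks 1-7: mean last rating 21.4/7 = 3.057; LOCF 2.864; 5.4% lost.
- Improvement complete by Week 4, all last ratings in Weeks 5-7: 0% lost.

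**Dropout that depends on the last rating.** Simulation with n = 134, SD 1.2, correlation 0.5 + 0.5 x 0.7^lag, 25% dropout logistic in the last observed rating, and 1500 runs per case. The true Week 8 mean is 2.80; likelihood means use unstructured covariance and visit only.

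| Path | Log-odds of leaving per point | LOCF | Likelihood, observed cases |
|---|---|---|---|
| Linear | 0 | 2.955 | 2.800 |
| Linear | +1 (worse leave) | 3.067 | 2.802 |
| Linear | -1 (better leave) | 2.862 | 2.806 |
| Flat from Week 4 | 0 | 2.870 | 2.800 |
| Flat from Week 4 | +1 | 2.985 | 2.800 |
| Flat from Week 4 | -1 | 2.765 | 2.792 |

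LOCF error runs from -0.04 to +0.27 points, or -3% to +22% of the 1.2-point change; the likelihood mean stays within 0.01. Other ways of calibrating the dropout give about -0.05 to +0.32 for LOCF and at most about 0.02 for the likelihood mean. A plain mean of patients still observed at Week 8 ranges from about 2.6 to 3.0 in these cases, so an observed-case t-test would not be an adequate replacement.

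**The test itself.** At mean 2.95, SD 1.2, n = 134: t = (2.95 - 4)/(1.2/√134) = -10.1.

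**The case against.** The protocol's model could not be run as written, so the SAP had to change something. It chose the method both documents already use for the parallel scale, CGI-I, and the protocol uses LOCF for the PGI-I response rate. This explains the choice but does not make LOCF necessary. Protocol 9.3 brings LOCF in as an additional approach; for endpoint 11 the SAP makes it the only one.

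The size is uncertain. The trajectory, SD and correlation are assumed, and the range includes zero and a reversed sign. The likelihood mean does well partly because the simulated dropout is missing at random; no missing-not-at-random case was run, and Protocol 9.3 says that possibility cannot be excluded. These limits stand.

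The Efficacy Sample requires a post-baseline IDS-SR, so some Week 1 leavers may not be analysed. If all of them drop out, leavers are (0.25 x 6/7)/(0.75 + 0.25 x 6/7) = 22.2% of the set with mean last rating 3.325. The linear-path loss is then 0.222 x 0.525/1.20 = 9.7% instead of 12.5%, which is smaller but still present.

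The SAP's amendment history (Section 14) and table list (Appendix 2) are not in the text supplied, so a reason recorded there cannot be excluded. Section 10 is nevertheless the plan's heading for such changes, and it is wrong for this endpoint.

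Finally, endpoint 11 is nominal and unadjusted, and no decision turns on it. That limits the importance of the point but leaves the discrepancy in place.

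**Conclusion.** The concern holds. That the method was changed without being recorded in Section 10 is plain from the two texts and rests on no assumption. The effect on the estimate is conditional: with 25% dropout and steady improvement, LOCF understates the Week 8 change by about 10% to 19%; with an early plateau the error is 0% to about 5%; with rating-dependent dropout it runs from about -3% to +22%. The co-primary analyses and the sample size are unaffected, and the test against no change would probably give the same result. This should be corrected, but it does not threaten the trial's main conclusion.

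**What to change.** In SAP 8.2, analyse endpoint 11 by MMRM on observed cases with fixed effects for diary week (Weeks 1 to 8, as windowed in SAP Table 11.1-2) and trial center, no PGI-I baseline terms, and unstructured covariance with the plan's fallback structures. Test each weekly least-squares mean against 4, and state that 4, the scale midpoint, is the no-change value. Because the OC dataset is defined by scheduled visits, add that windowed diary weeks count as visits for diary items; the SAP already uses the OC dataset for diary PGI-S in endpoint 13. Keep the LOCF t-test as supportive.

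In SAP Section 10, record the new endpoint wording, the dropped baseline terms and the reason. The protocol's change-from-baseline wording for PGI-I should be corrected as well; the Section 10 entry can carry the change until the protocol is amended. Using the same model for CGI-I is optional, since protocol and SAP agree on LOCF there.

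The cost is SAP wording, one Section 10 entry and one more call of a procedure already in use, with no new data. Only the protocol wording would need an amendment.
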